1.4.2. Phase 1 Study in Adolescents

In a Phase 1 study in adolescents (BB-IND 18170; sponsored by DMID and NIAID) 50 males and non-pregnant females ages 9 to 17 years old, inclusive are being enrolled. Subjects are randomized 1:1 to receive one 10^8 TCID₅₀ dose of Bris10 M2SR vaccine or placebo administered intranasally (IN) followed by one dose of licensed quadrivalent influenza vaccine (QIV) administered intramuscularly 3 months later. As of February 2019, 19 subjects have been enrolled (first subject first visit was in August 2018) and have received both dose treatments. These subjects have been followed through at least the Day 113 visit (21 days after administration of the QIV) with no reported SAEs, AEs of significance or halting rules met.

1.4.3. Phase 2a Challenge Study

The Phase 2a challenge study included 108 healthy male and non-pregnant female subjects ages 18-55 years old who had microneutralization titers (MNT) of ≤ 20 to H3N2 A/Belgium/4217/2015. Subjects were randomized 1:1 into two cohorts (Bris10 M2SR or Placebo) each receiving investigational product (IP) of either a 10^8 TCID₅₀ dose of Bris10 M2SR vaccine (N=48) or a saline control (N=51) under EudraCT 2017-004971-30. Approximately 28 days later, 99 of these subjects were challenged via intranasal inoculation with approximately 10^6 TCID₅₀ dose of an antigenically distinct H3N2 A/Belgium/4217/2015. The first subject first dose was in May 2018 and the last subject completed the Day 180 post-IP follow-up visit in March 2019. In the period following IP treatment (Day -28) until Day 1, there were no severe AEs or severe local or systemic complaints and there were no reported fevers ($\geq 38^\circ\text{C}$). The active phase of this Phase 2a challenge study has been completed and there were no SAEs, AEs of significance or observations that would halt the study. All subject samples (including serum, PBMC and nasal swabs for humoral, cellular and mucosal immunity, respectively) have been collected and are undergoing analytical testing. Nasal swabs collected for detection of influenza virus have been analyzed. The finalization and locking of the clinical database and final analyses are in process.

Preliminary results from the Phase 2a challenge study suggest that the vaccine was effective against challenge in subjects for whom a detectable serum immune response was measured after vaccination. Subjects who demonstrated any increase from baseline in serum antibody response ($\sim 50\%$ of the M2SR cohort) by MNT to the intranasal M2SR vaccine had lower viral load and influenza-like symptoms than placebo subjects. These preliminary results suggest that M2SR could potentially provide higher efficacy levels if a greater proportion of M2SR recipients can demonstrate an appropriate serological response. In an effort to increase the number of sero-responders to H3N2 M2SR, the Phase 1b study described in this protocol is planned to further optimize the dose and schedule for M2SR vaccinations. Subjects in the proposed Phase 1b study must have a MNT ≤ 20 to A/Singapore/INFIMH-16-0019/2016 in order to be enrolled.

Between the FTIH Phase 1 and the Phase 2a challenge studies, a total of 72 adult subjects have been exposed to the highest dose of Bris10 M2SR tested (10^8) with no SAEs or AEs of significance or observations that would halt these studies. In addition, in the challenge study, 48 subjects who received the live, single-replication M2SR virus were subsequently challenged with a live, replicating influenza virus. A portion of those individuals experienced

infection and symptoms consistent with influenza (e.g., nasal congestion, runny nose, sore throat, cough, tiredness, headache), but at frequency less than observed among individuals in the same study who did not receive vaccine prior to challenge. Of the 19 adolescents enrolled in the ongoing second Phase 1 study, while the randomization was set at 1:1 active to placebo, it is not known exactly how many received active investigational vaccine (M2SR), but in blinded review no safety concerns related to the M2SR vaccine have been reported. Combined, these findings indicate that the vaccine is safe and generally well tolerated as a single 10^8 TCID₅₀ dose.

1.5. Overall Rationale for the Study

Currently available inactivated and recombinant influenza vaccines primarily aim to induce neutralizing antibodies that recognize only the HA and depend on a close match between the vaccine and circulating viruses, rendering them much less effective against drift viruses. In addition, while a strong relationship has been established between pre-existing T cell immunity and illness severity, inactivated vaccines do not elicit cellular immune responses and therefore generally do not provide broadly cross-reactive (heterosubtypic) immunity needed to protect against divergent strains. For example, the severity of the 2014-15 influenza season was due, at least in part, to mismatch between the circulating epidemic strain and the inactivated vaccine, resulting in VE of just 13% (Paules 2018). Similarly, during the 2017 influenza season in Australia, the inactivated vaccines displayed a preliminary VE estimate of only 10%, again related to mismatch between the vaccine strain and the circulating seasonal H3N2 virus that had accumulated antigenic changes (i.e., “drifted”) (Paules 2018). These recent examples indicate the need for an influenza vaccine that can protect against seasonal influenza drift variants.

In contrast to currently available influenza vaccines, pre-clinical testing of M2SR vaccine has shown induction of broadly reactive immune responses against multiple influenza subtypes and heterosubtypic protection in animal models, including demonstration of robust systemic, cellular and mucosal immunogenicity (Sarawar 2016, Hatta 2017), even in the presence of pre-existing anti-influenza immunity. In a pre-clinical proof-of-concept study, Bris10 M2SR (one of the vaccines to be used in the current study) provided protection to ferrets against a drifted H3N2 challenge virus, A/Alaska/140/2015, a virus belonging to clade 3c.2a1. In addition, adult subjects who received Bris10 M2SR (10^8 TCID₅₀ dose) in the Phase 1a FTIH and Phase 2a studies demonstrated broad-spectrum immune responses. In the FTIH study, vaccine induced serum and mucosal antibody responses were cross-reactive against multiple antigenically different H3N2 viruses including recent strains that belong to the same clade (3c.3b) as the challenge virus used in the Phase 2a study (FluGen IB). In the Phase 2a study, early data suggest that the vaccine was effective against challenge with an antigenically drifted virus in subjects for whom a serum response to the vaccine was detected (data on file).

This Phase 2a dose escalation clinical study is designed to assess the safety, tolerability/reactogenicity, and immunogenicity of M2SR vaccines when delivered at higher dosages or in two doses to increase the proportion of subjects responding serologically to the vaccine. For this study, an updated vaccine, Sing2016 M2SR, has been prepared that will provide the HA and NA components from A/Singapore/INFIMH-16-0019/2016, the H3N2 strain recommended for the 2018-2019 influenza season.

1.6. Risk/Benefit Analysis

1.6.1. Potential Risks

In previously conducted trials, 72 adult subjects and 19 adolescents have been treated with Bris10 M2SR (or placebo in adolescents as the ongoing study is still blinded). No SAEs or AEs of significance have been reported. In the challenge study, 48 subjects who received the live, single-replication M2SR virus were subsequently challenged with a live, replicating influenza virus. A portion of those individuals experienced infection and symptoms consistent with influenza (e.g., nasal congestion, runny nose, sore throat, cough, tiredness, headache), but at frequency less than observed among individuals in the same study who did not receive vaccine prior to challenge. Combined, these findings indicate that the vaccine is safe and generally well tolerated as a single 10^8 TCID₅₀ dose.

As outlined in greater detail in the accompanying IB, the potential risks of vaccine administration are expected to be similar to those associated with other live attenuated influenza vaccines (such as FluMist). Subjects with contraindications to live vaccines, such as severe allergic reactions (e.g., anaphylaxis) after a previous dose of any influenza vaccine, and immunocompromised persons, are excluded from study participation. Severe risks known to be associated with vaccine administration include anaphylaxis. As with any experimental product, there may be unknown risks.

1.6.2. Potential Benefits

There are no expected benefits to individual subjects participating in this study. There is a need for an influenza vaccine that can protect against seasonal influenza drift variants. Bris10 M2SR administration has shown induction of broadly reactive immune responses against multiple influenza subtypes and heterosubtypic protection in animal models, including demonstration of robust systemic, cellular and mucosal immune, even in the presence of pre-existing anti-influenza immunity. This study is expected to provide important additional information to guide continued development of M2SR vaccine in a quadrivalent formulation with the aim of improving efficacy relative to currently licensed influenza vaccines.

2. STUDY OBJECTIVES AND ENDPOINTS

2.1. Study Objectives

2.1.1. Primary Objectives

The primary objectives are:

1. To assess the safety and tolerability of one and two administrations of the Bris10 M2SR influenza vaccine each at 10^8 TCID₅₀ delivered intranasally to healthy adult subjects.
2. To assess the safety and tolerability of one and two administrations of the Sing2016 M2SR influenza vaccine each at 10^8 , $10^{8.5}$ and 10^9 TCID₅₀ delivered intranasally to healthy adult subjects

2.1.2. Secondary Objectives

The secondary objectives are:

1. To assess the immunogenicity (serum antibody, mucosal antibody and cellular immune responses) of one and two administrations of Bris10 M2SR vaccine at 10^8 TCID₅₀.
2. To assess the immunogenicity (serum antibody, mucosal antibody and cellular immune responses) of one and two administrations of Sing2016 M2SR vaccine at 10^8 , $10^{8.5}$ and 10^9 TCID₅₀.
3. To evaluate vaccine virus shedding after intranasal delivery.

2.1.3. Exploratory Objectives

The exploratory objectives are:

1. To evaluate cell mediated immunity for up to 2 months after the last vaccination.
2. To evaluate additional vaccine-related immune responses during the period of study participation.

2.2. Study Endpoints

2.2.1. Primary Endpoints

The primary endpoints are:

1. The number and percentage of study participants who experience any vaccine-associated AEs or SAEs after Bris10 M2SR or placebo administration.
2. The number and percentage of study participants who experience any vaccine-associated AEs or SAEs after Sing2016 M2SR or placebo administration.

2.2.2. Secondary Endpoints

The secondary endpoints are:

1. The number and percentage of study participants who after one or two doses of Bris10 M2SR or placebo demonstrate:
 - i. Influenza-specific serum antibody responses measured at specified time points;
 - ii. Influenza-specific mucosal immunoglobulin A (IgA) antibody responses measured at specified time points;
 - iii. Influenza-specific cellular immune responses measured by cytokine enzyme-linked immunospot (ELISPOT) at specified time points.
2. The number and percentage of study participants who after one or two doses of Sing2016 M2SR or placebo demonstrate:
 - i. Influenza-specific serum antibody responses measured at specified time points;
 - ii. Influenza-specific mucosal IgA antibody responses measured at specified time points;
 - iii. Influenza-specific cellular immune responses measured by ELISPOT at specified sampling time points.
3. Vaccine virus shedding evaluated by influenza A-specific qPCR on day 7 post IP administration.

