1.2.4. FluGen's H3N2 (A/Brisbane/10/2007) M2SR vaccine

FluGen is developing a novel live virus vaccine platform known as “M2SR” to address the need for more effective influenza vaccines that will provide more consistent and broad-spectrum immunity for adults, and especially the elderly. The product is a live virus vaccine for intranasal administration that has been shown to provide protection against multiple influenza A subtypes in animal models (see below). The vaccine is a replication-defective recombinant influenza virus that does not express the essential M2 protein (and hence, the derivation of the “M2SR” naming convention [Single Replication phenotype due to lack of M2]). The M2SR vaccine virus backbone is comprised of (1) five of the six internal proteins of the donor virus Influenza A/Puerto Rico/8/34 (PR8), a strain that has been used for decades in traditional inactivated influenza vaccine manufacturing; (2) the sixth internal protein, M2, which is acquired from the cell substrate used to grow the vaccine virus, M2 Vero cells, which stably express and supply M2 protein for vaccine virus growth; and (3) the two influenza virus surface protein antigens, HA and neuraminidase (NA), which can be derived from any selected Type A influenza strain. The resulting vaccine virus can infect normal cells in the respiratory epithelium of the vaccine recipient and then uncoat and initiate infection similar to a wild-type influenza virus, thereby evoking an immune response. However, because the M2SR genome does not encode for M2 protein, no viral progeny are subsequently produced after the initial (single round) infection, such that no cell-to-cell spread or subsequent shedding of virus occurs. The HA and NA of an A/Brisbane/10/2007-like H3N2 virus was chosen as the prototype monovalent vaccine to be initially tested in humans and is further referred to here as “Bris10 M2SR”.

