1.4.1. Phase 1 Dose Escalation Study

For the FTIH Phase 1 study, 96 healthy adult male and non-pregnant female subjects ages 18-49 years, were stratified by baseline hemagglutination-inhibition (HAI) antibody titers (<10 to 80) against influenza A/Brisbane/10/2007 (Bris10) and enrolled under US IND 016968 (also see ClinicalTrials.gov identifier NCT02822105). First subject first visit occurred in July 2016 and last subject last visit (Day 180) was in April 2017. Subjects were randomly assigned to receive either a single administration of Bris10 M2SR at dose levels of 10^6 , 10^7 or 10^8 TCID₅₀ (24 subjects per dose level) or saline placebo (N=24; 8 for each Bris10 M2SR dose group). Each subject received ~ 0.1 mL of vaccine or placebo intranasally (IN) in each nostril – except for the 10^8 group, who received 0.15 mL per nostril – using a mucosal atomization device (MAD) from the Teleflex VaxINator kit including a MAD301 sprayer. The vaccine was safe and well tolerated at all dose levels, generated a dose-response effect for humoral (hemagglutination-inhibition antibody) and mucosal antibodies against both homologous and heterologous influenza variants, and elicited robust T-cell responses. No infectious virus was detected in nasal swabs collected on Days 1, 2, 3 and 7 post-dose in any vaccinated subject. One subject in the 10^7 dose cohort and one subject in the placebo cohort self-reported fevers as high as 38.2°C (day 7 post-dose) and 38.4°C (day 3 post-dose), respectively. Subjects were followed through Day 180 post-dose. There were no severe local or systemic reactions recorded on subject 7-day diaries, no reported serious adverse events (SAEs) or adverse events (AEs) of significance (attributed to the treatment) and none of the pre-specified halting rules (including laryngospasm, bronchospasm or anaphylaxis) were met.

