Each subject will undergo the following testing (also depicted in [Table 3](#)): [Note that a Pre-screen with blood draw to assess the subject's microneutralization (MN) titer to Sing2016 may be conducted under a site-specific ICF in the period spanning 90 calendar days before enrollment in this study.] Subjects who meet eligibility criteria will be enrolled in the proposed Phase 1b study, have a baseline blood draw, be randomized to a dose cohort and administered IP of either active M2SR vaccine or placebo on Days 1 (Visit 01) and 29 (Visit 04). For 7 days following each dose the subjects will record symptoms in a Symptom Memory Aid ([Appendix 5](#)) and after 3 days (Days 4 and 32) will be contacted via a phone call by the site staff representative to report symptoms and AEs. Subjects will attend the investigational site for follow-up on Days 8, 29, 36, 57 and 209 (Visits 03, 04, 06, 07 and 08, respectively) for a limited physical exam, safety evaluation, nasal swabs and blood draws. Day 209 will also be the end of study visit for each subject in the study. Serum samples for analysis of anti-HA antibody titers for the H3N2 antigen in Sing2016 and Bris10 will be collected at baseline and on Days 8, 29, 36, 57 and 209. PBMC samples for analysis of cell-mediated immunity and/or innate transcriptome gene expression will be collected at baseline and on Days 4 (optional), 8, 29, 32 (optional), 36 and 57 from select sites for ~160 subjects. Nasal swabs will be collected on Days 1, 8, 29, 36, 57 and 209 for analysis of IgA-specific anti-HA antibody titers. Nasal swabs will be collected at Days 1, 8, 29, and 36 to evaluate shedding of vaccine virus. A nasal swab collected at Day 1 may be evaluated for presence of respiratory pathogens. Safety clinical laboratory testing will be performed at screening, and on Days 1, 8, 29, and 36. During the treatment period (Day 1 – Day 57), subjects will be asked to notify the site immediately if symptoms of influenza (fever, chills, sore throat, rhinorrhea, cough, muscle/body aches) occur. When increased influenza infections are being reported in the geographic region of the investigational site, subjects will additionally be contacted at Days 15±2, 21±2, 43±2, and 50±2 by phone or messaging. If influenza is suspected the subject will be asked to return to the site for laboratory confirmation of influenza using nasal swabs.

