6.1.2.6. Day 36 (7 days -1/+7 day after second dose)

- Perform limited physical examination
- Vital signs (blood pressure, heart rate, and temperature)
- Collect blood for serum chemistry and hematology
- Urinalysis (dipstick)
- Symptom Memory Aid reviewed
- Nasal swab into buffer for mucosal IgA and virus shedding
- Collect blood sample for humoral immunogenicity assays (MNT and other serum assays)
- Collect blood sample (PBMC) for cellular immunogenicity assays (ELISpot) – only by select sites
- Collect blood sample (plasma) for cytokine expression – only if PBMC collected by site
- Record concomitant therapy/AEs/SAEs

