6.2.4. Efficacy Evaluations

6.2.4.1. Nasal Swabs

Nasal swabs will be collected from subjects for the following purposes:

1. To determine mucosal immunity
2. To test for the presence of shedding influenza virus
3. To test for the presence of respiratory viruses and bacteria (Optional)

Nasal swabs will be collected at the time points specified in the Schedule of Events ([Table 3](#)) from all subjects. Individual swabs will be collected from each nostril and combined into a single vial of media. Samples will be aliquoted to use in various tests.

To evaluate mucosal immunity, an ELISA-based test will be used to measure 1) mucosal IgA antibody titer to HA and 2) total IgA concentration

To detect shedding influenza virus, a quantitative H3N2 RT-PCR assay will be used. Only swabs that have a positive qRT-PCR test result will be subjected to quantitative infectious culture assay.

Possible infection with respiratory viruses and bacteria may be evaluated by use of a qualitative PCR test. This multiplexed assay will be performed by use of a commercial, qualitative viral and bacterial upper respiratory tract infection panel PCR device (adventitious agent screening).

If a subject presents within 7 days of vaccination with symptoms of fever, upper respiratory illness, nephritis/cystitis, conjunctivitis or diarrhea, regardless of the severity of the symptoms, an additional nasal swab(s) should be collected and/or analyzed outside of the defined time points.

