8.2.1. Secretory IgA Immune Response and Viral Shedding from Nasal Swab

Summary statistics for secretory IgA immune response (influenza A-specific and total IgA ELISA) at Days 1 (baseline), 29, and 57 post IP administration will be provided.

Summary statistics for viral shedding (influenza A-specific q-PCR) at Screening, Days 1 and 8, will be provided.

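### The first scheduled shedding swab comes about 7 days after each dose, so a negative result does not address earlier shedding, and the SAP leaves out dose 2 and the few early swabs

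*Protocol*

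**What the plan says.** The secondary objective (Protocol 2.1.2) is general: "To evaluate vaccine virus shedding after intranasal delivery". The matching endpoint (Protocol 2.2.2) names one time: "Vaccine virus shedding evaluated by influenza A-specific qPCR on day 7 post IP administration".

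On sampling, Protocol 3.2 states: "Nasal swabs will be collected at Days 1, 8, 29, and 36 to evaluate shedding of vaccine virus". In Table 3 the Day 1 and Day 29 swabs are taken before dosing, and Days 4 and 32 have no swab. Day 8 has a window of ±1 day. Section 6.1.2.6 gives the visit after dose 2 as "Day 36 (7 days -1/+7 day after second dose".

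Two provisions can produce unscheduled early swabs. Protocol 6.2.4.1 asks for an extra swab under a condition that begins "If a subject presents within 7 days of vaccination with symptoms of fever, upper respiratory illness" and continues with other symptoms. Protocol 3.2 and 6.1.3 call for swabs when influenza is suspected between Day 1 and Day 57.

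The SAP plan (8.2.1) is one sentence: "Summary statistics for viral shedding (influenza A-specific q-PCR) at Screening, Days 1 and 8, will be provided". It mentions neither Day 36 nor the unscheduled swabs. SAP section 12 records that shedding data were not available at database lock and may be analysed later.

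On the first-in-human Bris10 trial, Protocol 1.4.1 reports: "No infectious virus was detected in nasal swabs collected on Days 1, 2, 3 and 7 post-dose in any vaccinated subject".

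**The concern.** The objective covers shedding after delivery in general, but scheduled sampling starts about a week after each dose. Protocol 1.2.4 describes a virus for which "no viral progeny are subsequently produced after the initial (single round) infection". If that holds, the days soon after dosing are the natural place to look for virus leaving the nose. The earlier Bris10 trial looked there; this one does not, and neither document gives a reason for the change.

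Uncertainty rose at the same time. Sing2016 M2SR had not been given to humans before, carries nine amino acid changes in its backbone, and is given at up to 10^9 TCID50. The earlier maximum was 10^8, with Bris10.

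What is at stake is interpretation. A row of zeros at Day 8 could be taken as evidence that the new vaccine is not shed, when it bears directly only on persistence to about day 7. Because the SAP summary stops at Day 8, a two-dose study would also have no planned shedding summary after the second dose.

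**Working it through.** The documents give no power, precision or sample-size figure for shedding (50 per group is empirical, Protocol 8.3.1), so there is no stated figure to reproduce.

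**1. Time of the first scheduled post-dose swab.**
- Dose 1: Day 8 ±1, with dosing on Day 1, gives 7 ± 1 = 6 to 8 days.
- Dose 2: 7 days, −1/+7, gives 6 to 14 days. Protocol 6.2.1.6 describes this visit as ±1 day, which would give 6 to 8; the two passages should be reconciled.
- Scheduled swabs before day 6: none here, against three (Days 1, 2 and 3) in the earlier trial.

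**2. Dose relative to the earlier maximum of 10^8.**
- Sing2016 10^8 and Bris10 10^8: 1 times.
- Sing2016 10^8.5: 10^0.5 = 3.16 times.
- Sing2016 10^9: 10 times, in one of the four active arms.

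**3. What zero positives at day 7 would bound.** Let p be the share of an arm that ever sheds and f the share of those still PCR-positive at the day-7 swab. The value of f is an assumption; the documents give none. The swab observes p × f. With 0 of n positive, the exact one-sided 95% upper bound on p × f is 1 − 0.05^(1/n), so the bound on p is [1 − 0.05^(1/n)] / f.
- n = 50 (planned): 1 − 0.05^(1/50) = 5.8%.
- n = 40 (approximate actual, SAP section 12): 1 − 0.05^(1/40) = 7.2%.

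| Assumed f | Bound on p, n = 50 | Bound on p, n = 40 |
|---|---|---|
| 1 | 5.8% | 7.2% |
| 0.5 | 11.6% | 14.4% |
| 0.25 | 23.3% | 28.9% |
| 0.1 | 58.2% | 72.2% |
| 0.05 | none (exceeds 100%) | none (exceeds 100%) |

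**4. Chance of seeing any positive.** If p = 20% (assumed), the chance of at least one day-7 positive is 1 − (1 − 0.2f)^n.
- n = 50: 99.5% at f = 0.5, 63.6% at f = 0.1, 9.5% at f = 0.01.
- n = 40: 98.5%, 55.4% and 7.7%.

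The answer depends almost wholly on f. As f approaches 0, the sample sizes here do not make up for the timing.

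**5. Coverage in the SAP.** Protocol 3.2 schedules shedding swabs on Days 1, 8, 29 and 36. SAP 8.2.1 summarises Screening, Day 1 and Day 8. The only post-dose-2 sample in that schedule, Day 36, is missing. Screening is included, although Table 3 aliquots that swab for IgA only.

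**The case against.** The best defence is that the endpoint is honest about its timing. It names day 7, the analysis is descriptive, and the objective is only to evaluate shedding. Day 7 is also a defensible choice: PCR soon after instilling up to 10^9 TCID50 may detect residual inoculum, whereas a later swab tests persistence. PCR may stay positive longer than culture, so f need not be near zero. All of this stands. It limits what may be claimed, but it supplies no information about the days before day 6.

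Several stronger readings are tempting, and the documents do not support them:
- **That the trial plans to claim no shedding.** No passage does so.
- **That outpatient conduct depends on this endpoint.** Protocol 3.2 bases it on the earlier and ongoing Bris10 trials.
- **That day 7 cannot detect shedding at all.** That needs f near 0. Assumed RNA half-lives of 6, 12 or 24 hours would give falls from day 3 to day 7 of 2^16 = 65,536, 2^8 = 256 or 2^4 = 16 times. Without a starting level and a detection limit, these say nothing about detectability.
- **That infectious virus is not sought.** Protocol 6.2.4.1 sends every PCR-positive swab to culture, a normal screen-then-confirm order.
- **That the earlier trial is a like-for-like comparison.** Its reported result is for infectious virus; this endpoint is PCR.
- **That no early samples can exist.** Symptom-triggered and influenza-suspicion swabs may fall in the first week, but they miss asymptomatic shedders.

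It is also fair that new swabs look impracticable in this trial: by the SAP date enrolment had stopped and Day 209 calls had taken place.

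**Conclusion.** The point holds as a limit on interpretation together with a gap in the SAP. A negative shedding result means that vaccine RNA was not detected about 7 days after dosing, and no more. Its weight as evidence on ever shedding runs from a 5.8% upper bound (0 of 50, f = 1) to no bound at all (f of 0.05 or less). The documents do not say where in that range the trial lies. The bounds assume an exact binomial count within one arm and a single f for all shedders in it. The tenfold dose step concerns the 10^9 arm only; the absence of scheduled early sampling concerns every arm. The omission of Day 36 from the SAP needs no assumption: it follows from setting SAP 8.2.1 beside Protocol 3.2.

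**What to change.** In SAP 8.2.1:
1. Report the result as RNA detected or not detected about 7 days post-dose, with the actual day of sampling, and draw no conclusion on the absence of earlier shedding. The endpoint already says day 7, so the gain lies in the stated limit.
2. Add the symptom-triggered and influenza-suspicion swabs taken within 7 days of each dose, by arm and day. Label them a symptomatic subset that cannot estimate a shedding rate. Include placebo: the assay is described as influenza A-specific or H3N2, and neither description says that it separates vaccine from wild-type virus. State which assay these swabs receive, since Protocol 6.2.4.1 does not.
3. Include the scheduled Day 36 swab, so that dose 2 is covered.

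Because shedding data were outstanding at lock, these changes can still be made before the later analysis.

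Where dosing is still to come, which in practice probably means a later study, take a shedding aliquot from subjects already attending the optional Day 4 and Day 32 visits. Report them as a self-selected subset in which an early PCR positive may reflect residual inoculum.

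The cost is a small assay load, one minor swab at each visit already attended, and a narrower claim.
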